## Appendix 8 Clinical Global Impression

Category	Change in modified JDA severity index total score for GPP	and/or	Category description
Very much improved	Reduction by 3 or >points	or	Clear or almost clear of signs of GPP
Much improved	Reduction by 1 or 2 points	or	At least one of the following: 
 
• Area of erythema with pustules (%) reduced by <math>\leq 30\%</math>
 
or
 
• Clinically meaningful improvement in at least 2 other components of the modified JDA severity index for GPP (area of erythema, area of edema, fever, WBC, CRP, Alb)
 

Minimally improved	0 points (no change)	and	At least one of the following: 
 
• Area of erythema with pustules (%) reduced by <math>\leq 20\%</math>
 
or
 
• Clinically meaningful improvement in at least 1 other components of the modified JDA severity index for GPP (area of erythema, area of edema, fever, white blood cell [WBC], C-reactive protein [CRP], Alb)
 

No change	0 points (no change)	and	Not meeting the other criteria of “minimally improved”
Worsened	$\geq + 1$ point	-	Not applicable

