5. STUDY DESIGN

5.1. GENERAL DESCRIPTION

This is an open-label, single arm, multiple dose study to assess the clinical efficacy, as well as the safety, tolerability, and PK of multiple doses of ANB019 in subjects with GPP.

The screening period will be up to 42 days (6 weeks) prior to administration of study drug on Day 1. Written informed consent will be obtained from each subject prior to initiating any study related procedures. All screening procedures will be conducted in accordance with the Schedule of Activities (see Section 1.3 in the protocol). On Day 1, subjects who meet the entry criteria will receive a 750 mg IV dose of ANB019 in an open-label manner, followed by 3 doses of 100 mg SC administered on Days 29, 57, and 85.

Subjects will leave the study center after completion of the 5 hours postdose assessments following IV administration and the 3 hours postdose assessments after the first and second SC injections and with the investigator's approval. Subjects with any ongoing AEs or SAEs at the time of scheduled discharge from the study center should remain at the study center until the Investigator has determined that these events have resolved or are deemed as not clinically significant.

After completing Day 1 assessments, the subjects will return to the study center for follow-up visits on Days 3, 8, weekly from Day 8 to Day 29, every other week up to Day 85, then monthly for 12 weeks to monitor changes in disease activity, safety, and tolerability. In addition, subjects will be contacted via phone by study staff to assess for safety (e.g., AEs and changes in concomitant medications) on Days 36, 50, 64, and 78.

Subjects who are non-responders at Week 4 will be early terminated 4 weeks after the 750 mg IV dose administration. A non-responder is defined as a subject who experiences:

- "No change" on Clinical Global Impression (CGI): 0 points change in JDA total score and not meeting "other criteria" for minimally improved.
- "Worsened" based on CGI: ≥1-point increase in JDA total score.

[figure not shown]
Disease activity (response to study treatment) will be evaluated using the CGI scale according to the mJDA severity index, change in total area of erythema with pustules, erythema, and edema as measured by modified JDA index, systemic manifestations and laboratory findings as per modified JDA severity index, GPPPGA scale, and PASI score (if PP is present). Quality of life (QoL) will be assessed using the DLQI.

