8.6.2. PERCENT CHANGE FROM BASELINE AT VISIT X

Percent change from Baseline at Visit X will be calculated as follows:

Percent change from Baseline = (Test value at Visit X – Baseline value) / Baseline value x 100

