17. EFFICACY OUTCOMES

17.1. PRIMARY EFFICACY

17.1.1. RESPONSE BASED ON CLINICAL GLOBAL IMPRESSION SCALE

The primary efficacy endpoint is the proportion of subjects achieving clinical response at Weeks 4 and 16. The clinical response is defined as a composite score which considers both the CGI and reduction in the mJDA score (compared to Baseline) at that visit, and is classified as "Very much improved", "Much improved", or "Minimally improved" on the 5-point CGI scale (see **Table C. Clinical Global** Impression).

Page 10 of 43

Table C. Clinical Global Impression

Change in mJDA Severity Index Total score	and/ or	CGI Category description	CGI scale and Responder status
Reduction by 3 or >3 points	or	Clear or almost clear of signs of GPP	Very much improved
			Responder
Reduction by 1 or 2 points	or	At least one of the following: Area of erythema with pustules (%) reduced by ≤30%, or Clinically meaningful improvement in at least two other components of the mJDA severity index for GPP (area of erythema, area of edema, fever, white blood cells (WBC), C-reactive protein (CRP) and serum albumin (Alb)).	Much improved Responder
0 points (no change)	and	At least one of the following: Area of erythema with pustules (%) reduced by ≤20%, or Clinically meaningful improvement in at least one other component of the mJDA severity index for GPP (area of erythema, area of edema, fever, WBC, CRP, Alb)	Minimally improved Responder
0 points (no change)	and	Not meeting the CGI criteria of "minimally improved"	No change Non- responder
Increased $\geq + 1$ point		Not applicable	Worsened Non- responder

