17.1.2. MISSING DATA METHODS FOR PRIMARY EFFICACY VARIABLE

If the Responder Status is missing for a subject due to Lost to Follow-Up or early discontinuation or any other reason, it will remain missing.

Subjects who are non-responders (i.e. rated as "No change" or "Worsened" on CGI) at Week 4 will be early terminated from the study. Their Responder Status at Week 16 will remain non-responder.

If the Baseline mJDA severity index total score is missing, Responder Status will be defined based on CGI alone.

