17.2. SECONDARY EFFICACY

17.2.1. SECONDARY EFFICACY VARIABLES & DERIVATIONS

17.2.1.1. Change in mJDA Severity Index Total Skin Lesions Score At All Study Visits

The mJDA severity index is used to determine the primary endpoint, but itself is not a primary efficacy

variable. Individual components of the mJDA severity index are used for secondary efficacy analysis. Table D shows the mJDA questionnaire.

Table D. Modified Japanese Dermatological Association (mJDA) Worksheet

	Score	Score						
	0	1	2	3				
Assessment of skin lesions	Assessment of skin lesions							
Area of erythema with pustules	0%	>0%, <10%	≥10%, <50%	≥50%				
Total area of erythema	0%	>0%, <25%	≥25%, <75%	≥75%				
Area of edema	0%	>0%, <10%	≥10%, <50%	≥50%				
Assessment of systemic manife	stations and lal	ooratory findings						
Fever (°C)	<37.0	≥37.0, <38.5	≥38.5	n/a				
WBC count (/µL)	<10 000	≥10 000, <15 000	≥15 000	n/a				
CRP (mg/dL)	< 0.3	≥0.3, <7.0	≥7.0	n/a				
Serum albumin (g/dL)	≥3.8	<3.8,≥3.0	<3.0	n/a				

The scores (0 to 3 for skin lesions, and 0 to 2 for systemic manifestations and laboratory findings) as well as the actual values of all seven mJDA assessments will be captured in the eCRF.

The total score will be calculated as follows and is the sum of these 7 scores:

Severity Index Total Score = Sum of scores for: Area of erythema with pustules, Total area of erythema, Area of edema, Fever, WBC count, CRP, Serum albumin The severity index total score will be categorized as follows in the listings: 1-6 = Mild, 7-10 =

Moderate, and 11-17 = Severe.

Severity Index Total score at Visit X = Sum of all 7 mJDA scores at Visit X.

Severity Index Total score at Baseline = Sum of all 7 mJDA Baseline scores.

Change at Visit X = Severity Index Total score at Visit X – Severity Index Total score at Baseline

Descriptive statistics (including n, mean, SD, median, minimum, and maximum) will be presented for each measurement time for all study visits. Each subject's change in mJDA Severity Index Total score will be plotted over all study visits.

The change from Baseline in the mJDA severity index total skin lesions score is the sum of erythema, erythema with pustules, and edema scores. The change in score for each visit can range from -9 to 9 and will be calculated as follows:

Total Skin Lesions Score at Visit X = Sum of the scores at Visit X for: Area of erythema with pustules, Total area of erythema, Area of edema.

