Total Skin Lesions Score at Baseline = Sum of the scores at Baseline for: Area of erythema with pustules, Total area of erythema, Area of edema.

Change at Visit X = Total Skin Lesions Score at Visit X – Total Skin Lesions Score at Baseline

Descriptive statistics (including n, mean, SD, median, minimum, and maximum) will be presented for each measurement time for all study visits. Each subject's change in mJDA total skin lesion score will be plotted over all study visits.

17.2.1.2. Change in Affected Area of Erythema With Pustules, Erythema, and Edema at All Study Visits

The change from Baseline in each of the measurements: percent area of erythema, percent area of erythema

with pustules, and percent area of edema at all study visits will be calculated.

The change for each visit for each area percentage will be calculated as follows:

Area % at Visit X = The percentage from the mJDA assessment.

Area % at Baseline = Total percentage from the mJDA assessment at Baseline

Change at Visit X = Area % at Visit X – Total area % at Baseline

Descriptive statistics (including n, mean, SD, median, minimum, and maximum) will be presented at each measurement time for all study visits. An overlay plot of each subject's value over all study visits will be presented for each component score.

17.2.1.3. Change in Total and Individual Scores in Systemic Manifestations and Laboratory Findings as Measured by mJDA Severity Index at All Study Visits

The change from Baseline of the total and the four individual scores in systemic manifestations and laboratory findings, as measured by the mJDA at all study visits, will be summarized in the same manner as the change in mJDA severity index total skin lesions score.

Change in the total score for each visit can range from -8 to 8 and will be calculated with the following derivations:

Total score at Visit X = Sum of scores at Visit X for: Fever, WBC count, CRP, Serum albumin Total score at Baseline = Sum of scores at Baseline for: Fever, WBC count, CRP, Serum albumin Change at Visit X = Total score at Visit X – Total score at Baseline

Change in the four individual scores for each visit can range from -2 to 2 and will be calculated as follows:

Fever Score Change at Visit X = Fever Score at Visit X – Fever Score at Baseline

The same formula will be applied to calculate the **Score Change at Visit X** for the **WBC Count, CRP** and **Serum albumin**.

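### The pustule-area criteria in the primary response table are ceilings (≤30%, ≤20%) where floors are needed, so a large reduction can be rated *No change* while a trivial one counts as a response

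*SAP*

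**What the plan says.** SAP 17.1.1, Table C, assigns the five CGI categories from the change in mJDA total score together with a category description.

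- *Much improved* (responder): a fall of 1 or 2 points **or** at least one listed criterion. The first is "Area of erythema with pustules (%) reduced by ≤30" per cent; the other is meaningful improvement in at least two other components.
- *Minimally improved* (responder): no change in total score **and** at least one of "Area of erythema with pustules (%) reduced by ≤20%, or Clinically meaningful improvement in at least one other component".
- *No change* (non-responder): no change in total score and the criteria for *Minimally improved* not met.
- *Worsened* (non-responder): a rise of at least 1 point.

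Protocol Appendix 8 has the same structure, with "Area of erythema with pustules (%) reduced by" followed by ≤30% and ≤20% in the two rows. No other section of either document states a minimum reduction or an order of precedence between categories.

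Protocol 4.1 and SAP 5.1 terminate non-responders 4 weeks after the IV dose and define worsening as "≥1-point increase in JDA total score". For subjects rated *No change* or *Worsened* at Week 4, SAP 17.1.2 adds: "Their Responder Status at Week 16 will remain non-responder".

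Neither table says how the percentage is calculated. SAP 8.6.2 gives a relative formula, "Percent change from Baseline = (Test value at Visit X – Baseline value) / Baseline value x 100". SAP 17.2.1.2 takes a plain difference for these same areas, "Change at Visit X = Area % at Visit X – Total area % at Baseline".

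**The concern.** A graded improvement scale needs a minimum for each grade. Here the area criteria set a maximum, so at an unchanged total score a bigger improvement is more likely to miss them. The mJDA bands for pustular area are wide (10% to below 50% scores 2; 50% and above scores 3), so a large fall need not move the score. The area criteria appear meant to pick up exactly those cases.

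The responder proportion at Weeks 4 and 16 is the main efficacy result. The rating also determines conduct: *No change* at Week 4 removes the subject from the study and is carried to Week 16, so one inverted sign can count the same subject as a failure twice. SAP 17.1.4 plans no sensitivity analysis, and SAP 7.2 allows interim data to guide protocol changes and later studies.

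**Working it through.** **Inputs.** Area ceilings of 30% and 20% and the category logic: SAP Table C and Protocol Appendix 8. Pustular-area bands: SAP Table D (>0 to <10% scores 1; ≥10 to <50% scores 2; ≥50% scores 3). Sample size of about 10: SAP 5.2. The plan gives no figure of its own to reproduce.

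**Conditions held throughout.** (a) mJDA total unchanged; (b) skin not clear or almost clear; (c) no clinically meaningful improvement in another component. Under these, the category depends on pustular area alone.

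**Formulas.** Relative reduction = 100 × (baseline − follow-up) / baseline. Absolute reduction = baseline − follow-up, in area points.

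**Examples, each staying inside one band:**

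| Pustular area | Relative | Absolute | As written | With ≥30% / ≥20%, relative |
|---|---|---|---|---|
| 45% → 12% (score 2 both times) | 33/45 = 73.3% | 33 points | Fails ≤30 and ≤20: *No change*, non-responder | *Much improved*, responder |
| 45% → 44% (score 2 both times) | 1/45 = 2.2% | 1 point | Meets both: responder | *No change*, non-responder |
| 90% → 65% (score 3 both times) | 25/90 = 27.8% | 25 points | Meets ≤30, so *Much improved*; fails ≤20, so also *No change* | *Minimally improved*, responder |

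The results as written are the same on the relative and absolute readings. The third row is a conflict in responder status: *Much improved* can be reached through its *or*, *No change* requires only that *Minimally improved* is not met, and nothing says which prevails.

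**How much of the possible range is affected.** I counted every whole-number decrease that stays inside one band. A band with n whole values has n(n − 1)/2 such pairs: 9 × 8/2 = 36, 40 × 39/2 = 780 and 51 × 50/2 = 1275.

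| Band | Pairs | Fails both area criteria, relative (>30%) | Fails both, absolute (>30 points) | Conflict, relative (>20 to 30%) | Conflict, absolute (>20 to 30 points) |
|---|---|---|---|---|---|
| 1–9% | 36 | 27 | 0 | 4 | 0 |
| 10–49% | 780 | 450 (58%) | 45 (6%) | 113 (14%) | 145 (19%) |
| 50–100% | 1275 | 309 (24%) | 210 (16%) | 284 (22%) | 255 (20%) |

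In the other direction, across the two upper bands (780 + 1275 = 2055 pairs), reductions below 20 that meet the area criteria as written but would be *No change* with floors number 884 on the relative reading and 1349 on the absolute reading.

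These counts show which values the rule misclassifies under conditions (a) to (c). They are not expected frequencies in patients.

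**Effect on the endpoint.** One misclassified subject out of about 10 moves the proportion by 1/10, or about 10 percentage points.

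**The case against.** **Narrow reach.** The large-reduction error needs all three conditions. One other improved component gives *Minimally improved*, two give *Much improved*, and any net 1-point fall in the total is a response. This stands, and the number affected may be small. The opposite error, a trivial reduction counted as a response, is easier to reach.

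**Clinical judgement.** SAP 17.1.2 speaks of subjects being rated, and an Investigator is unlikely to call 45% → 12% no change. That may limit the harm, but Protocol 8.1.1 ties the category to the mJDA total and Appendix 8. A site that follows the table gets the wrong answer, and a site that silently corrects it departs from the protocol. With 8–10 centres and about 10 subjects, raters may differ for nearly every subject.

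**Top-down reading.** Reading the table from best to worst resolves the 20–30% conflict in favour of response. That is sensible, but neither document says so, and it does not help reductions above 30%. Treating the ceilings as upper limits of graded bands also fails: a reduction above 30% short of almost clear then has no category but *No change*.

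**Exploratory study, data visible.** There is no hypothesis test, and areas and CGI categories are plotted by subject, so misclassification could be noticed. This stands for the analysis, but not for a subject already terminated at Week 4.

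**Intent is inferred.** The documents do not state that ≥ was meant. This stands, and the sponsor should confirm it. A text-extraction fault is unlikely: both documents show ≤ in these rows and a correct ≥ in the *Worsened* row.

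**Conclusion.** The concern holds, and the table must be corrected. As written, the area criteria reverse the intended order at an unchanged mJDA total, on either reading of the percentage, in the table that defines the sole primary efficacy endpoint and triggers Week 4 termination. They also leave reductions above 20% and up to 30% in a responder and a non-responder category at once.

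The conclusion rests on the literal wording of both tables and on conditions (a) to (c). How many subjects meet those conditions cannot be derived from the documents. No alpha or power is affected, since the analysis is descriptive.

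**What to change.** In SAP Table C and Protocol Appendix 8:

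1. Change the pustular-area criteria to reductions of ≥30% (*Much improved*) and ≥20% (*Minimally improved*), once the sponsor confirms the intent.
2. State that the percentage is relative to Baseline, as in SAP 8.6.2. In absolute points, a subject whose baseline pustular area is below 20% could never meet either floor.
3. Add one line: the best category met applies, except that a rise of 1 point or more in the mJDA total is always *Worsened*. Without the exception, the *or* in the *Much improved* row could override a rise in total score. The exception only carries over what Protocol 4.1 and SAP 5.1 already say.

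The drafting is small, but Appendix 8 is protocol text, so the change needs an amendment with ethics and, where applicable, regulatory approval (Protocol Appendix 2). For data already collected, the area criteria can be re-derived, because "the actual values of all seven mJDA assessments will be captured in the eCRF". Clinically meaningful improvement is undefined and stays a recorded judgement. Week 16 outcomes cannot be recovered for anyone already terminated at Week 4, which is a reason to act promptly. No change to the stopping rule itself is proposed.

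A separate clerical point: the SI brackets for CRP in Protocol Appendix 9 should read 70 mg/L, not 70 mg/dL. SAP Table D is already correct.

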17.1.2. MISSING DATA METHODS FOR PRIMARY EFFICACY VARIABLE

If the Responder Status is missing for a subject due to Lost to Follow-Up or early discontinuation or any other reason, it will remain missing.

Subjects who are non-responders (i.e. rated as "No change" or "Worsened" on CGI) at Week 4 will be early terminated from the study. Their Responder Status at Week 16 will remain non-responder.

If the Baseline mJDA severity index total score is missing, Responder Status will be defined based on CGI alone.

17.1.3. ANALYSIS OF PRIMARY EFFICACY VARIABLE

This is an exploratory study and no formal hypothesis testing will be performed. The primary efficacy analysis will be performed on the FAS (see Section 8). Descriptive summary statistics will be presented for the CGI. The number and proportion of subjects achieving clinical response will be summarized in tabular form for Weeks 4 and 16. Each subject's CGI category will be plotted over all study visits.

The proportion of subjects having a clinical response at Weeks 4 and 16 will be derived using all subjects randomized and enrolled as the denominator for this calculation.

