### **5.4 Screen Failures**

Screen failures are defined as subjects who consent to participate in the clinical study but are not subsequently enrolled in the study. A minimal set of screen failure information is required to ensure transparent reporting of screen failure subjects to meet the Consolidated Standards of Reporting Trials publishing requirements and to respond to queries from regulatory authorities. Minimal information includes demography, screen failure details, eligibility criteria, and any SAE.

Individuals who do not meet the criteria for participation in this study (screen failure) may be rescreened once after discussion with Medical Monitor. Rescreened subjects should not be assigned the same subject number as for the initial screening.

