6. STATISTICAL GENERAL CONSIDERATIONS

All data listings, summaries, and analyses will be performed under the guidance and approval of the Sponsor with this SAP.

Coding of AEs and medical history will be done by Medical Dictionary for Regulatory Activities (MedDRA) directory Version 22 (or higher) and medications data by the World Health Organization (WHO)-drug dictionary dated Mar2019 (or higher) by

The default summary statistics for continuous variables include number of contributing observations (n), mean,

standard deviation (SD), median, minimum, and maximum or as described in the respective section. For categorical variables, the number and percentage (the percentage of subjects in each category relative to the total number of subjects in the relevant analysis set, or relative to the total number of subjects in the relevant analysis set and with assessments available [where appropriate]) in each category will be the default summary presentation.

In general, for non-PK data, the number of decimal places displayed for each statistic will be determined as follows:

- Mean and median: 1 more than the number of decimal places allotted in the raw data received from data management.
- SD: 2 more than the number of decimal places allotted in the raw data.
- Minimum and maximum: equal to the number of decimal places allotted in the raw data.
- Percentages: All percentages between 0 and 100 will be rounded to 1 decimal unless there is a need to report more than 1 decimal for percentages.
- Reference ranges will be reported to the same number of decimal places displayed by the laboratory.
- *P* values and confidence intervals (CIs), if any, will be reported to 4 decimal places. *P* values less than 0.0001 will be presented as "<0.0001" and *p* value greater than 0.9999 will be presented as "1.0000".

Data from subjects excluded from an analysis set will be included in the data listings, but not in the summaries. Concentration versus time summaries will be presented for all subjects in the PK Analysis Set (PKAS). Reporting standards for PK data (ANB019 concentrations) is described in Section 18.

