7.2. INTERIM ANALYSIS

An interim analysis will be performed when approximately 50% of subjects have completed their Week 4 visit or when at least 2 subjects have reached 16 weeks postdosing. The interim analysis will assess primary efficacy and all safety data. Data from interim analyses might be used as a guideline for possible protocol modifications and planning of future clinical studies.

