11. DISPOSITION AND WITHDRAWALS

All subjects who provided informed consent (ENR) will be accounted for in this study. Subject disposition will be listed and summarized, including:

- Total subjects screened
- Number of screen failures (subjects who consent to participate in the clinical study but are not subsequently entered in the study)
- Total of subjects in the FAS
- Total subjects ongoing (subjects ongoing at the time of the IA)
- Total number of subjects in the SAF
- Total number of subjects in the PPS
- Total number of subjects in the PK Analysis Set
- Total subjects who discontinue from study treatment
- Total subjects who discontinue from the study
- Protocol deviations (PD) as obtained from the CTMS PD log

PDs will be identified and discussed with the Investigator/AnaptysBio in PD review meetings to categorize them, and to finalize analysis set assignment.

A subject is considered to have completed the study if they have completed all scheduled study visits

including the last visit on Day 169.

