Descriptive statistics (including n, mean, SD, median, minimum, and maximum) will be presented at each measurement time at all study visits for each numeric systemic manifestation and laboratory finding. An overlay plot of each subject's value over study visits will be presented for each measurement at all study visits.

17.2.1.4. Proportion of Subjects Achieving A GPPPGA Score of 0 or 1 at Post-Baseline Study Visits

The GPPPGA is a physician-based assessment of GPP, performed at every visit (except phone calls). The severity and impact of the subject's erythema, pustules, and scaling/crusting of pustular psoriasis lesions is scored on a 5-point scale as shown below in **Table E. Scoring of** GPPPGA.

Score	Wording	Detailed description
0	Clear	Normal skin or post-inflammatory hyperpigmentation, no visible pustules, no scaling or crusting
1	Almost clear	Faint, diffuse pink or slight red erythema, low density occasional small discrete pustules (non-coalescent), superficial focal scaling or crusting restricted to periphery of lesions
2	Mild	Light red erythema, moderate density grouped discrete small pustules (non- coalescent), predominantly fine scaling or crusting
3	Moderate	Bright red erythema, high density pustules with some coalescence, moderate scaling or crusting covering most or all lesions
4	Severe	Deep fiery red erythema, very high-density pustules with pustular lakes, severe scaling or crusting covering most or all lesions

Table E. Scoring of GPPPGA

Statistical Analysis Plan

The GPPPGA will be summarized at each post-baseline visit for the proportion of subjects achieving a score of 0 or 1 as opposed to a 2, 3 or 4. The proportion of subjects having a GPPPGA score of 0 or 1 will be derived using all subjects randomized and enrolled as the denominator for this calculation.

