17.2.2. MISSING DATA METHODS FOR SECONDARY EFFICACY VARIABLE

If GPPPGA score is missing for a subject, for any reason, the score will not be imputed. Missing values for DLQI will be replaced using Last Observation Carried Forward (LOCF) for summarization of the results. All other missing values for secondary efficacy assessments will remain missing and not be imputed for any summary calculations.

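### At the interim, the all-enrolled denominator counts subjects not yet due as failures; the primary response rate also has no planned confidence interval

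*SAP*

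**What the plan says.** - **Denominator.** SAP 17.1.3 runs the primary analysis on the FAS, and the proportion is "derived using all subjects randomized and enrolled as the denominator for this calculation". SAP 17.2.1.4 has the same rule: "The proportion of subjects having a GPPPGA score of 0 or 1 will be derived using all subjects randomized and enrolled as the denominator". The FAS (SAP Table A, Protocol Table 3) takes in all subjects, treated or not. The study is single arm, and Protocol 6.3 marks randomization as not applicable.
- **Missing status.** Under SAP 17.1.2, if responder status is missing through loss to follow-up, "early discontinuation or any other reason, it will remain missing". The one explicit exception is that Week 4 non-responders, who are terminated early, keep that status at Week 16. For the secondary endpoint SAP 17.2.2 says: "If GPPPGA score is missing for a subject, for any reason, the score will not be imputed".
- **General default.** SAP 6 allows percentages on the whole analysis set or "relative to the total number of subjects in the relevant analysis set and with assessments available [where appropriate".
- **Interim.** SAP 7.2 plans a look "when approximately 50% of subjects have completed their Week 4 visit or when at least 2 subjects have reached 16 weeks postdosing". It covers primary efficacy and all safety data, and may inform protocol modifications and future studies.
- **Precision.** Protocol 9.4 asks for two-sided 95% intervals with point estimates where applicable. SAP 5.4 declares no departure from the protocol analysis. SAP 17.1.3 gives number and proportion only.

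**The concern.** A fixed all-enrolled denominator suits a completed study. At a look taken while subjects are still moving through the schedule, it mixes two kinds of subject without a result: those who reached the visit and have no status, and those who have not reached it. The first kind can reasonably count as non-response. The second kind says nothing about the drug, yet lowers the rate just as much. The interim rate may inform changes to this protocol and the planning of later studies, so a rate pulled down by enrolment timing could mislead those decisions.

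Two smaller matters go with this. The statement that missing status stays missing, together with the SAP 6 default, leaves some room for an observed-case rate. That rate would tend to lean upward: a Week 4 responder later withdrawn for adding systemic psoriasis medication (Protocol 6.5.1) would leave the denominator. And with about 10 subjects, a percentage without an interval hides how little it pins down.

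**Working it through.** The documents give no response rate, dropout rate or interim enrolment count, so there is no plan figure to reproduce. From the documents: planned N of about 10, the interim triggers, and the denominator rule. All other counts below are assumptions.

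**1. Interim.** Literal rate = responders so far / all enrolled. Its ceiling = number assessed at the visit / all enrolled. I take 50% of the planned 10, so 5 assessed at Week 4, and for the other trigger 2 assessed at Week 16. The number enrolled by the cut-off is varied.

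| Enrolled at cut-off | Week 4 ceiling | Week 4 literal, 4 of 5 respond | Week 4 among those due | Week 16 ceiling |
|---|---|---|---|---|
| 10 | 5/10 = 50% | 4/10 = 40% | 4/5 = 80% | 2/10 = 20% |
| 7 | 5/7 = 71% | 4/7 = 57% | 4/5 = 80% | 2/7 = 29% |
| 5 | 5/5 = 100% | 4/5 = 80% | 4/5 = 80% | 2/5 = 40% |

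The distortion at a visit vanishes when everyone enrolled is due there, as at Week 4 with 5 enrolled. If the 50% in SAP 7.2 means half of those enrolled by then, the Week 4 ceiling under that trigger is about 50% whatever the number.

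**2. Week 4 non-responders carried to Week 16.** They acquire a Week 16 status 12 weeks before continuing subjects do. Assume 5 past Week 4 (4 responders, 1 non-responder), of whom 2 responders have reached Week 16 and respond there. If the non-responder is entered at once, the rate is 2/3 = 67%. If the same due rule applies to everyone and that subject's Week 16 window is still open, it is 2/2 = 100%, with an exact lower limit of 0.025^(1/2) = 16%. The due rule therefore has to cover carried subjects too.

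**3. Final analysis.** Assume 10 enrolled and dosed, 2 Week 4 non-responders, m missing at Week 16 after later withdrawal, and the rest responders (8 − m).

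| m | As written | Missing stated as non-response | Observed cases | Gap |
|---|---|---|---|---|
| 0 | 8/10 = 80% | 8/10 = 80% | 8/10 = 80% | 0 |
| 1 | 7/10 = 70% | 7/10 = 70% | 7/9 = 78% | 8 points |
| 2 | 6/10 = 60% | 6/10 = 60% | 6/8 = 75% | 15 points |
| 3 | 5/10 = 50% | 5/10 = 50% | 5/7 = 71% | 21 points |

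Columns two and three are identical, so stating the rule changes no final number. The gap column assumes that every continuing subject responds, which makes it as large as it can be for each m. With 2 missing and one continuing non-responder it is 5/10 = 50% against 5/8 = 62.5%, or 12.5 points.

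**4. Interval.** Clopper-Pearson limits for x of n are the 2.5% quantile of Beta(x, n − x + 1) and the 97.5% quantile of Beta(x + 1, n − x). For 6/10 = 60% they are 26.2% and 87.8%. For an interim 4/5 = 80% they are 28.4% and 99.5%.

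**The case against.** The plan does name a denominator. SAP 17.1.3 and 17.2.1.4 are specific to these endpoints and take precedence over the SAP 6 default, which applies only where appropriate. Leaving a status missing fits that rule: the value stays blank in listings while the subject stays in the denominator. This stands. A reader might infer that the final response rate is left open between an all-enrolled and an observed-case value, but the documents favour the all-enrolled one.

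A reader might also infer that screen failures enter the denominator, because SAP 11 says "All subjects who provided informed consent (ENR) will be accounted for in this study". That is strained. SAP 11 counts screen failures separately from the FAS, and Protocol 5.4 says: "Screen failures are defined as subjects who consent to participate in the clinical study but are not subsequently enrolled in the study". With nobody randomized, the stray word reduces the phrase to enrolled subjects, so deleting it is editorial.

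On the interim, SAP 8 requires agreement on analysis-set membership beforehand, and SAP 11 reports subjects still ongoing. Neither solves the problem. An ongoing subject not yet at Week 4 belongs in the FAS as defined, so the gap is a visit-level rule and not a question of set membership. It is fair that no stopping rule hangs on this look and that its size depends on enrolment.

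On the interval, Protocol 9.4.4.1 asks only for number and percentage, and Protocol 9.4 qualifies its request. A reader might infer a breach of the protocol; the qualifier does not support that. It remains a useful addition at almost no cost.

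Denominators must be shown or footnoted (SAP Appendix 1), CGI categories are plotted by subject and data are listed, so a reader could recompute either rate. That discloses the choice but does not fix it in advance. The table templates, which I have not seen, may settle some of this.

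**Conclusion.** The point holds for the interim analysis. If 10 subjects are enrolled at the cut-off, the literal rule caps the response rate at 50% at Week 4 with 5 assessed and at 20% at Week 16 with 2 assessed, whatever the drug does. With fewer enrolled the cap rises, and it disappears once everyone enrolled is due at the visit. Actual interim enrolment is not in the documents.

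At the final analysis the rule as written already treats missing status as non-response. The observed-case reading is the weaker one and only needs closing off. In the assumed example with 2 of 10 missing it would give 75% instead of 60%, and with nothing missing the two agree.

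The missing interval is a secondary gap. Severity is minor: the study is exploratory, tests no hypothesis, and no error rate is affected.

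**What to change.** In SAP 17.1.3 and 17.2.1.4, with matching words in 17.1.2 and 17.2.2:

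- **Interim denominator.** Restrict each visit's numerator and denominator to enrolled subjects whose window for that visit has closed by the data cut-off, whether or not they are still in the study. Count from Day 1, or from the enrolment date if never dosed. With the ±2-day windows in SAP Table B, Week 4 closes after Day 31 and Week 16 after Day 115. Apply the same restriction to Week 4 non-responders carried to Week 16.
- **Interval.** Report a Clopper-Pearson 95% confidence interval for the response proportion at Weeks 4 and 16.
- **Clarification.** Delete 'randomized', and state that missing status at a due visit counts as non-response (for GPPPGA, as not achieving 0 or 1).
- **Optional.** Show observed cases as a supportive row. SAP 17.1.4, which plans no sensitivity analysis, would then need a matching edit.

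The cost is a few SAP sentences, one table column and slightly more programming. No new data are needed if an enrolment date is recorded for never-dosed subjects, which the documents do not confirm. Subjects seen a day or two before their window closes drop out of that interim rate unless the cut-off is set to allow for it. The stated rule also gives a lower headline rate than observed cases whenever status is missing.
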